## **6.4. COMMON CALCULATIONS**

For quantitative measurements, change from Baseline will be calculated as:

- Change from Baseline = Test value at visit X – Baseline value

## **6.5. SOFTWARE VERSIONS**

### **6.5.1. ALL ANALYSES EXCEPTION OF PK ANALYSIS**

All analyses will be conducted using SAS version 9.4 or higher.

[figure not shown]
### **6.5.2. PK ANALYSIS**

Non-compartmental PK parameter calculations will be performed using Phoenix® WinNonlin® 6.4 or higher (Certara, Princeton, New Jersey). Graphics may be prepared using SAS version 9.4 or higher, or Phoenix WinNonlin, or with SigmaPlot 12.5, or higher (Systat Software, Inc., San Jose, California).

## **7. STATISTICAL CONSIDERATIONS**

### **7.1. MULTICENTER STUDIES**

This study will be conducted by multiple investigators at multiple centers in the United States. Data from all investigational centers will be pooled for all analyses.

## 7.2. MISSING DATA

Missing or partially missing concomitant medication and adverse event (AE) start and stop dates will be imputed as described in APPENDIX 1. However, imputed dates will NOT be presented in the listings, as their sole purpose will be for the classification of the medications as prior, concomitant, or post-treatment (refer to Section 13) and the classification of AEs as prior, treatment-emergent, or post-treatment (refer to Section 17.1.1).

Missing data for ESS total score will be imputed as specified in Section 16.1.1 and missing data for the Movement Disorders Society-Unified Parkinson's Disease Rating Scale (MDS-UPDRS) Parts III total score will be imputed as specified in Section 16.2.1.2.

All other missing data will not be imputed.

## 7.3. ADJUSTMENTS FOR COVARIATE AND FACTOR TO BE INCLUDED IN ANALYSES

The following covariate will be used in the efficacy analyses. For details of their inclusion in the models, see the specific analysis Section (i.e., Section 16.1.4).

- Baseline value of efficacy endpoint

## 7.4. MULTIPLE COMPARISONS/ MULTIPLICITY AND SIGNIFICANCE LEVELS

Given the exploratory nature of this study, there will be no adjustment for multiple testing.

[figure not shown]
## 7.5. EXAMINATION OF SUBGROUPS

Exploratory analyses of efficacy endpoints ESS, MWT, PGIc, CGIc will be conducted for the following subgroups of subjects:

- Age ( $\leq 65$  years old and  $> 65$  years old)
- Gender (males vs. females)
- ESS total score at Baseline ( $<$  median and  $\geq$  median)
- Mean sleep latency on the MWT at baseline ( $< 30$  minutes and  $\geq 30$  minutes) for each definition
- Use of any dopamine agonist at baseline (yes and no)

For all other efficacy endpoints, subgroup analyses will only be conducted for Age and Gender.

If there are 10 or less than 10 subjects within a given subcategory of a subgroup, only descriptive statistics will be provided. That is, no analysis will be performed for that subgroup.

## 8. OUTPUT PRESENTATIONS

APPENDIX 2 shows conventions for presentation of data in outputs. The table, figure, and listing (TFL) shells provided with this SAP describe the presentations for this study and therefore the format and content of the summary tables, figures and listings to be provided by [REDACTED].

## 9. DISPOSITION AND WITHDRAWALS

[figure not shown]
The number and percentage of subjects randomized in each treatment group, randomized in each enrollment group, completing/withdrawing across all treatments and safety follow-up periods including reason for withdrawal, receiving at least one dose overall and in each treatment period, and completing/withdrawing overall and from each study period (i.e, Period 1, Period 2, Period 3, and Period 4) including reason for withdrawal, will be presented by sequence based on the RND.

Critical and major protocol deviations as classified in the clinical trial management system (CTMS) will be summarized according to the following categories and presented overall and by sequence based on the RND:

- Administrative Criteria
- Concomitant Medications Criteria
- Efficacy Criteria
- Eligibility and Entry Criteria
- Investigational Product Compliance
- Informed Consent Criteria
- Laboratory Assessment Criteria
- Randomization Criteria
- Regulatory or Ethics Approvals Criteria
- Serious adverse event (SAE) Criteria
- Source Document Criteria
- Study Procedures Criteria
- Visit Scheduled Criteria
- Other Criteria

All protocol deviations will be listed.

Inclusion and exclusion from each analysis population, including reasons for exclusion (see Section 5.4 for the reasons of exclusion from the PP) will be summarized by sequence based on the RND.

## 10. DEMOGRAPHIC AND OTHER BASELINE CHARACTERISTICS

[figure not shown]
Demographic and other Baseline characteristics will be summarized using descriptive statistics for the SAF overall and by sequence. Similar summaries will also be presented for the mITT and PP by treatment group (including all JZP-110 doses pooled into one group) and broken down further by sequence for the placebo treatment group.

[figure not shown]
Demographic and other Baseline characteristics include:

- Age (years) - calculated relative to date of signed informed consent
- Birth gender
- Race
- Ethnicity
- Weight (kg)
- Height (cm)
- BMI (kg/m^2)
- Creatinine clearance (CLcr) at screening (mL/min) as calculated by the central lab using the Cockcroft-Gault Formula ([FDA Guidance for Industry. Pharmacokinetics in Patients with Impaired Renal Function – Study Design, Data Analysis, and Impact on Dosing and Labeling, May 1998](#); refer to Section 10.1)
- Baseline ESS total score
- Baseline average sleep latency time (minutes) on the MWT for each type of sleep latency
- Baseline MDS-UPDRS Part III total score, Part IV total score, Part IV dyskinesia subcomponent score, Part IV motor fluctuations subcomponent score, and Part IV dystonia subcomponent score
- Baseline apathy total score, cognitive-behavioral subscale score, and general apathy subscale score
- Baseline FSS total score
- Baseline SCOPA-Cog total score, memory subscale score, attention subscale score, executive functions subscale score, visuo-spatial functions subscale score

### 10.1. DERIVATIONS

- Age (years) = largest integer less than or equal to [(date of informed consent – date of birth) + 1]
- BMI (kg/ m^2) = weight (kg)/ height (m)
- CLcr (mL/min) = 
$$\frac{[140 - \text{age (years)}] * \text{weight (kg)} * (0.85 \text{ if female})}{72 * \text{serum creatinine (mg/dL)}}$$

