### 4.2 Inclusion Criteria

Each subject must meet the following criteria to be enrolled in this study.

1. Willing and able to provide written informed consent.
2. Males and females  $\geq 35$  and  $\leq 80$  years of age at the time of consent.
3. Diagnosis of idiopathic PD according to the UK PDS Brain Bank Criteria. NOTE: Having  $>1$  affected relative is not exclusionary for diagnosis of idiopathic PD for purposes of this protocol.
4. Hoehn and Yahr stage 1, 2, or 3 (see Part III in [Appendix 14](#)).
5. Must be on a stable treatment regimen for PD including dopaminergic therapy, monoamine oxidase B (MAO-B) inhibitors, COMT inhibitors, amantadine, and medications for treatment of non-motor symptoms including depression, for at least 4 weeks prior to screening, with no anticipated need to adjust these medications for the study duration. Amantadine use is not allowed if used solely for the treatment of excessive sleepiness.
6. ESS score  $>11$  at both Screening and Baseline visits. Any subject who is on a wake promoting agent or stimulant at screening will only have to meet the ESS score  $>11$  requirement at the Baseline visit, after they have washed out of their wake promoting agent or stimulant (see [Section 5.7](#)).
7. This criterion was removed in Amendment 2.
8. Body mass index  $\geq 17$  and  $\leq 40$  kg/m^2.
9. Consent to use a medically acceptable method of contraception for at least 2 months prior to the first dose of study drug, throughout the entire study period, and for 30 days after the study is completed (see Section 4.3 for medically acceptable methods).
10. Willing and able to comply with the study design schedule, all study procedures, and other requirements.
11. This criterion was removed in Amendment 2.

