### 11.1. DERIVATIONS

[figure not shown]
- Time since PD diagnosis (years) =  $[(\text{date of the signature of the ICF} - \text{date of diagnosis}) + 1] / 365.25$ . For partial dates, if day is missing, calculate the duration using the month and year at the event and screening:  $[(\text{month/year of the signature of the ICF} - \text{month/year of diagnosis}) + 1] / 12$ . If day and month are missing, calculate the duration using the year at the event and screening:  $(\text{year of the signature of the ICF} - \text{year of diagnosis}) + 1$ .
- Time since onset of sleep disorder (years) =  $[(\text{date of the signature of the ICF} - \text{sleep disorder start date}) + 1] / 365.25$ . For partial dates, if day is missing, calculate the duration using the month and year at the event and screening:  $[(\text{month/year of the signature of the ICF} - \text{month/year of sleep disorder start date}) + 1] / 12$ . If day and month are missing, calculate the duration using the year at the event and screening:  $(\text{year of the signature of the ICF} - \text{year of sleep disorder start date}) + 1$ .
- Time since resolution of sleep disorder (years) =  $[(\text{date of the signature of the ICF} - \text{sleep$

disorder end date) + 1] / 365.25. For partial dates, if day is missing, calculate the duration using the month and year at the event and screening: [(month/year of the signature of the ICF – month/year of sleep disorder end date) + 1] / 12. If day and month are missing, calculate the duration using the year at the event and screening: (year of the signature of the ICF – year of sleep disorder end date) + 1.

- To compute the total daily LED (mg) of each subject at Baseline, all PD motor symptoms-related medications that have been taken by a subject on the day of the first dose of study drug will be identified. The total daily dose of each of these medications will then be converted into a LED by applying the LED conversion factor as per Table 5 (Smith et al., 2010; Cervantes-Arriagal et al., 2009, GSK prescribing information for RequipXL, revised 2/2018; Rytary prescribing information, revised 1/2015). Lastly, the sum of the converted total daily LED dose of each subject's Baseline disease-related medications will be calculated.

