### **16.1.6. SUBGROUP ANALYSES OF KEY EFFICACY ENDPOINT**

Subgroup analyses will be performed for the key efficacy endpoint ESS, MWT, PGIc, CGIc for the age, gender, mean sleep latency time (minutes) on MWT as per each definition, and use of dopamine agonist at Baseline subgroups. For other key efficacy endpoints, subgroup analyses will be performed for age and gender only. (see Section 7.5) Subgroup having more than 10 subjects in each subcategory will be analyzed similarly to the key efficacy analysis while only descriptive statistics will be provided for subgroup having 10 or less than 10 subjects in any subcategory. Forest plot of the treatment difference in change from baseline to the end of the treatment period in ESS total score for each subgroup having more than 10 subjects will also be provided based on the mITT.

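### The SAP's age derivation omits the conversion from days to years; applied literally it spoils the age rows of the demographic tables and empties the younger age subgroup, although the intent is clear

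*SAP*

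**What the plan says.** SAP section 10 lists age among the demographic variables: "Age (years) - calculated relative to date of signed informed consent". Section 10.1 gives the derivation. It opens with the integer function, "Age (years) = largest integer less than or equal to", and with its argument it reads: "Age (years) = largest integer less than or equal to [(date of informed consent – date of birth) + 1", after which the bracket closes and the line ends. No divisor follows. Neither document gives another age formula, and SAP section 3.6, which lists changes from the protocol, does not mention age.

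SAP section 11.1 derives time since Parkinson's disease diagnosis, time since onset of a sleep disorder and time since its resolution, all in years. For complete dates each is a date difference plus 1, divided by 365.25. The last of them reads "disorder end date) + 1] / 365.25".

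Age is used again as an exploratory efficacy subgroup. Section 7.5 sets the cut: "Age ( $\leq 65$ years old and $> 65$ years old". Section 16.1.6 applies it: "Subgroup analyses will be performed for the key efficacy endpoint ESS, MWT, PGIc, CGIc for the age, gender". Section 7.5 also keeps age for the remaining endpoints: "For all other efficacy endpoints, subgroup analyses will only be conducted for Age and Gender". Section 16.2.5 narrows this by excluding subscale scores.

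The protocol's eligible range (section 4.2) is "Males and females $\geq 35$ and $\leq 80$ years of age at the time of consent".

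**The concern.** The label says years and the formula yields days. This is the only age rule a programmer is given, and it feeds two sets of outputs: the demographic tables for the safety, mITT and per-protocol populations, and the split at 65 years for the age subgroup. If the rule were followed as printed, the age rows of those tables would be meaningless and one side of the split would have no subjects. If it is silently overridden, the program and the SAP disagree, and the programmer has to choose a replacement that the SAP does not specify.

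**Working it through.** The plan states no figure to reproduce, so the check applies the rule to the eligible range.

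**Inputs.** Age rule: SAP 10.1. Divisor: 365.25, from SAP 11.1. Eligible range: 35 to 80 years, protocol 4.2. Subgroup cut: 65 years, SAP 7.5. Small-subgroup rule: SAP 16.1.6. Assumption: an illustrative consent date of 1 March 2018, falling on the subject's birthday. Another date would move the day counts by a day or so at most and would not change the classification.

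**Literal rule.** D = (consent date − birth date) + 1, then the integer part of D. D is already a whole number, so the integer step changes nothing.

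**With the divisor.** Integer part of D / 365.25.

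| True age | D (literal result) | D / 365.25 | Integer part |
|---|---|---|---|
| 35 | 12,785 | 35.003 | 35 |
| 50 | 18,263 | 50.001 | 50 |
| 65 | 23,742 | 65.002 | 65 |
| 66 | 24,107 | 66.001 | 66 |
| 80 | 29,221 | 80.003 | 80 |

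If the upper limit is read as completed years, a subject one day short of 81 is still eligible and has D = 29,585.

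**Subgroup.** The smallest literal value for an eligible subject is about 12,785, far above 65. So 100% of subjects fall in the over-65 category and 0% in the other.

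**Small-subgroup rule.** Section 16.1.6 restricts a subgroup to descriptive statistics if any of its subcategories has 10 or fewer subjects. Zero is below that limit, so the whole age subgroup for ESS becomes descriptive, including the over-65 side.

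**Does dividing by 365.25 fully repair it?** Nearly. Because of the added 1, the result can reach the next integer one day early. With 1 March 2018 as the consent date, a subject turning 35 the next day has D = 12,784, and 12,784 / 365.25 = 35.0007, which gives 35 instead of 34. Taking every birthday in 2017 and 2018 (730 dates) and placing consent on the day before, the formula already returns the new age in 730 of 730 cases at 35, 424 of 730 at 66 and 59 of 730 at 81. Two days before the birthday, and on the birthday itself, it was correct in every case. The case at 66 is the one that can move a subject across the subgroup cut.

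**The case against.** The best defence is that nobody would follow the rule literally. The unit is given as years in sections 10 and 10.1 and in the subgroup cut. An integer function has no purpose unless a division comes first. The creatinine clearance formula in the same list subtracts age in years from 140, and would be negative with age in days. A tabulated age above 12,000 would conflict at once with the protocol's range of 35 to 80. All of this stands: it is an omission whose intent can be recovered from the SAP itself, and that holds the severity down. It does not make the printed derivation correct.

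A reader might infer more than the documents support, in four ways:

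- *Every efficacy endpoint is affected.* Section 16.2.5 excludes subscale scores from subgroup analysis, so the reach is narrower than the broad sentence in section 7.5 suggests.
- *Only the younger category loses its analysis.* For ESS, section 16.1.6 makes the whole subgroup descriptive when any subcategory is too small.
- *The main ESS result is at risk.* The model in section 16.1.4 uses baseline ESS, treatment, sequence and period, with a random subject effect. Age is not in it.
- *Eligibility or creatinine clearance is at risk.* The protocol states its age criterion in years, and protocol section 6.10.1 and SAP section 10 assign the clearance calculation to the central laboratory.

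It is also possible that the divisor was lost when the PDF was read. That cannot be excluded, but the closing bracket is intact, the divisions for BMI and creatinine clearance survive in the same section, and 365.25 survives in section 11.1.

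**Conclusion.** The point holds at low severity. The age derivation in SAP section 10.1 lacks the conversion to years that its counterparts in section 11.1 have. Taken literally, it returns values of about 12,785 to 29,221 at ages 35 to 80, makes age in the demographic tables wrong, puts all subjects on one side of an exploratory subgroup cut, and reduces the age subgroup analysis of ESS to description. No conclusion about the primary objective or the main ESS comparison depends on it. The finding rests on the text as available being complete at that line, and the size given is that of literal application, which is unlikely in practice.

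**What to change.** Preferred: define age as completed calendar years at the date of informed consent. This gives the correct integer on every day of the year and leaves nothing ambiguous at the boundary between 65 and 66.

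At minimum: take the integer part of [(date of informed consent − date of birth) + 1] / 365.25, matching the structure of section 11.1, and note that it can be one year too high for a subject who consents on the day before a birthday.

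Either is a one-line change to the SAP, with the age variable programmed to match. It has no effect on trial conduct, data collection or sample size.

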## 11. PARKINSON'S DISEASE AND SLEEP DISORDERS HISTORY

Parkinson's disease and sleep disorders (i.e., restless legs syndrome [RLS], REM sleep behavior disorder [RBD], sleep-onset insomnia, sleep-maintenance insomnia, excessive [daytime] sleepiness, obstructive sleep apnea [OSA], periodic limb movement disorder) history will be summarized for the SAF overall and by sequence. Parkinson's disease and sleep disorders history variables include:

[figure not shown]
- Time since diagnosis for idiopathic PD (years)
- Hoehn & Yarh stage at Baseline
- Clinician Global Impression of Severity (CGIs)
- Use of anti-parkinsonian drug(s) at Baseline: none, dopamine agonists only, levodopa only, combination of dopamine agonists and levodopa
- Total daily Levodopa Equivalent Dose (LED) (mg) at Baseline
- For each sleep disorder:
  - Subjects who had, who still exhibit or who never had the sleep disorder
  - For subjects who had or who still exhibit the sleep disorder:
    - Time since onset of sleep disorder (years)
    - Time since resolution of sleep disorder (years)
  - For subjects who had or who still exhibit excessive daytime sleepiness, the timing of the start of this sleep disorder in comparison with the use of dopaminergic therapy (i.e., before or after use of dopaminergic therapy)

Total scores for the Berlin sleep apnea questionnaire, Questionnaire for Impulsive-Compulsive Disorders in Parkinson's Disease-Rating Scale (QUIPS-RS), and Beck Depression Inventory-2 (BDI-2) questionnaire (assessed at screening only) will be provided in subjects' data listing only.

### 11.1. DERIVATIONS

[figure not shown]
- Time since PD diagnosis (years) =  $[(\text{date of the signature of the ICF} - \text{date of diagnosis}) + 1] / 365.25$ . For partial dates, if day is missing, calculate the duration using the month and year at the event and screening:  $[(\text{month/year of the signature of the ICF} - \text{month/year of diagnosis}) + 1] / 12$ . If day and month are missing, calculate the duration using the year at the event and screening:  $(\text{year of the signature of the ICF} - \text{year of diagnosis}) + 1$ .
- Time since onset of sleep disorder (years) =  $[(\text{date of the signature of the ICF} - \text{sleep disorder start date}) + 1] / 365.25$ . For partial dates, if day is missing, calculate the duration using the month and year at the event and screening:  $[(\text{month/year of the signature of the ICF} - \text{month/year of sleep disorder start date}) + 1] / 12$ . If day and month are missing, calculate the duration using the year at the event and screening:  $(\text{year of the signature of the ICF} - \text{year of sleep disorder start date}) + 1$ .
- Time since resolution of sleep disorder (years) =  $[(\text{date of the signature of the ICF} - \text{sleep$

disorder end date) + 1] / 365.25. For partial dates, if day is missing, calculate the duration using the month and year at the event and screening: [(month/year of the signature of the ICF – month/year of sleep disorder end date) + 1] / 12. If day and month are missing, calculate the duration using the year at the event and screening: (year of the signature of the ICF – year of sleep disorder end date) + 1.

- To compute the total daily LED (mg) of each subject at Baseline, all PD motor symptoms-related medications that have been taken by a subject on the day of the first dose of study drug will be identified. The total daily dose of each of these medications will then be converted into a LED by applying the LED conversion factor as per Table 5 (Smith et al., 2010; Cervantes-Arriagal et al., 2009, GSK prescribing information for RequipXL, revised 2/2018; Rytary prescribing information, revised 1/2015). Lastly, the sum of the converted total daily LED dose of each subject's Baseline disease-related medications will be calculated.

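### SAP 11.1 adds a whole year to PD and sleep-disorder durations when only the event year is known, so these descriptive durations are overstated

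*SAP*

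**What the plan says.** SAP 11.1 (Derivations) gives three versions of each duration, according to how much of the event date is known. All count back from signature of the informed consent form (ICF).

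- **Complete date:** the difference in days, plus one, divided by 365.25.
- **Day missing:** the difference in months, plus one, divided by 12. For sleep-disorder resolution this reads "month/year of the signature of the ICF – month/year of sleep disorder end date) + 1] / 12".
- **Day and month missing:** "If day and month are missing, calculate the duration using the year at the event and screening", and the formula for resolution is "year of the signature of the ICF – year of sleep disorder end date) + 1".

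The bullets for time since PD diagnosis and time since sleep-disorder onset have the same three versions, including the same year-only rule.

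On use, SAP 11 states that this "history will be summarized for the SAF overall and by sequence", where SAF is the safety population. SAP 7.3 lists one covariate for the efficacy analyses: "Baseline value of efficacy endpoint".

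**The concern.** In the complete-date rule the added one is a day, which is ordinary inclusive counting and negligible on a scale of years. The two partial-date rules keep the added one but change its unit, first to a month and then to a year. The same history then gives a different duration depending only on how completely the date was recorded.

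These durations describe who was enrolled: how long subjects had had PD and how long they had had each sleep disorder, including excessive sleepiness. An error that always goes in one direction does not average out across subjects. The by-sequence columns are also small (planned 21, 21 and 7 in SAP 3.1, Table 1), so a chance imbalance in date completeness could look like an imbalance in disease duration.

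**Working it through.** **Inputs.** The three formulas come from SAP 11.1. The documents give no worked figure to reproduce, no distribution of event or consent dates, and no proportion of year-only dates. The dates below are illustrative, and dates spread evenly within a calendar year are an assumption.

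**One history under the three rules.** Event 15 June 2010, consent 15 June 2017 (2557 days):

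- complete date: (2557 + 1) / 365.25 = 7.00 years
- month and year: (84 + 1) / 12 = 7.08 years
- year only: (2017 − 2010) + 1 = 8 years

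**Against the longest possible duration.** Consent 15 March 2018, event some time in 2013:

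| Event date | Complete-date rule | Month-year rule | Year-only rule |
|---|---|---|---|
| 10 Jan 2013 | 5.18 | 5.25 | 6 |
| 1 Jul 2013 | 4.71 | 4.75 | 6 |
| 20 Dec 2013 | 4.24 | 4.33 | 6 |

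The earliest possible event, 1 January 2013, gives (1899 + 1) / 365.25 = 5.20 years. The year-only rule reports 6, which no date in 2013 can produce.

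**General form.** Let k be consent year minus event year, f the fraction of the consent year elapsed at signature, and g the fraction of the event year elapsed at the event.

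- True duration = k + f − g
- Year-only value = k + 1
- Error = (k + 1) − (k + f − g) = 1 − f + g

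Both f and g lie between 0 and 1, so the error runs from 0 to 2 years and is never negative. The true duration is at most k + f, which does not exceed k + 1; the two meet only for an event on 1 January with consent on 31 December, to within a leap day.

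**Average error, event in an earlier year (k of 1 or more).**

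- With g uniform, the mean is 1 − f + 0.5 = 1.5 − f: 1.5 years for early-January consent, 1.0 mid-year, 0.5 for late December.
- With f uniform as well, the mean is 1.5 − 0.5 = 1.0 year. Against the SAP's own complete-date rule it is 1.0 − 1/365.25 = 0.997 year.

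**Average error, event in the consent year (k = 0).** The event must precede consent, so g is at most f. The mean true duration is then 1/3 year and the mean error is 1 − 1/3 = 0.67 year.

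**Month-year rule.** It adds 1/12 = 0.083 year, which is minor.

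**Simulation check.** With 2,000,000 draws for each of k = 0, 1, 3, 5 and 10, the mean year-only error was 0.667 for k = 0 and 1.00 for every other k. Single-subject errors ran from about 0 to 1.999 years.

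**Effect on a group mean.** If a proportion p of subjects have year-only dates in earlier years, the mean rises by about p × 1.0 year: 0.1 at 10%, 0.3 at 30%, 0.5 at 50%. These values of p are illustrations only. In Sequence C (planned n = 7), one such date moves the mean by about 1/7 = 0.14 year.

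**The case against.** The strongest reply is that nothing inferential depends on these variables. Duration is not a covariate (SAP 7.3), not a term in the ESS model (SAP 16.1.4) and not a subgroup factor (SAP 7.5), and the protocol sets no duration threshold for entry. The same rule applies in every sequence, so it does not systematically favour one. All of this stands. A reader might infer that the efficacy or safety comparisons are distorted; the documents do not support that.

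A second reply is that the added year may be meant to avoid reporting zero years since diagnosis. Inclusion criterion 5 requires a stable PD regimen for at least 4 weeks before screening, so zero would be implausible. The SAP does not give this reason. It could explain some adjustment for events in the consent year, but not a whole year for older events.

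A third reply is that simply deleting the added one is no clean cure. This also stands. The plain year difference averages zero error only when consent dates are spread over the year and the event is in an earlier year. Its mean error is +0.5 year for consent at the start of a year and −0.5 at the end. For same-year events it is 0 − 1/3 = −0.33 year.

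Finally, the documents do not show that any date was recorded as year only, so the effect on the reported tables is unknown and could be nil.

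**Conclusion.** The year-only rule is wrong as written for all three durations, and no other section corrects it: SAP 7.2 does not address these durations, and SAP Appendix 1 covers only adverse-event and medication dates. The reported value is at or above the longest duration consistent with the recorded year.

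Two stronger readings should be resisted. The first is that every year-only duration is too long by exactly one year. One year is an average that needs evenly spread dates and an event in an earlier year; it becomes about 0.5 to 1.5 years by consent date and about 0.67 year for same-year events. The second is that mean disease duration in this trial is overstated by some definite amount. That would need the proportion of year-only dates, which the documents do not give.

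This is a minor but clear-cut correction, confined to the baseline history tables for the safety population, overall and by sequence.

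**What to change.** In SAP 11.1, for all three durations:

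- if only the year is known, impute 1 July of that year;
- if month and year are known, impute day 15;
- put the imputed date into the complete-date formula with the actual ICF date, and truncate at zero.

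Add these durations to the exceptions in SAP 7.2, which otherwise rules out imputation.

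This is sounder than dropping the added one because it keeps the known consent date. For events in an earlier year the mean error is about 0 whatever the consent date, and the largest single error is about half a year. One limit remains: a year-only event in the consent year, with consent in the first half of that year, is reported as zero when the true value is somewhere under half a year.

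The cost is a change of wording and one derivation. Reported durations become slightly shorter. Data collection and the inferential analyses are unchanged.
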